### 4.2.2 Analysis of continuous variables

Mean and SD will be provided at all available points in time for all valid values and after imputation. Imputation variables will include all data from the same “category” of secondary endpoints along with age and sex. If the imputation methods should fail to converge, then imputation variables will be successively removed starting with those having the weakest absolute value for linear correlation.

Variables at T1/T0WL will be analysed with linear models having the same structure as for the primary endpoint, but will include all three randomization arms from the outset (i.e. will not make use of the closed testing principle). Here too the variables will be shifted as with the primary endpoint.

Data for T0, T1 and T2 will be analysed for the intervention groups in a mixed model in which the stratification variables, time and group will be treated as fixed effects including the interaction between group and time. The patient ID will be treated as a random term. The model will be fit using restricted maximum likelihood (REML) and an unstructured variance-covariance matrix.

If multiple sub-scales of a questionnaire are tested formally, then Bonferroni-Holm correction for multiplicity will be used.

---

 The original German reads „In wie vielen dieser Situationen, in denen Sie zu viel gegessen haben, hatten Sie das Gefühl, die Kontrolle über Ihr Essverhalten verloren zu haben (während des Essens)?“

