### 7.4.4 Sample size calculation

Based on a conservative effect size of 0.55 (compared to 0.65 quoted above), a t-test will have 80% power if 63 patients are analyzed (42 in the pooled intervention groups and 21 in the waiting control group), as determined using the software PASS 11. The width of the confidence intervals for the difference in means between two groups can then be expected to be about 0.88 SD for the pooled variance. The covariates incorporated into the analysis methods mean that the true power can be expected to be somewhat higher than that of the t-test reported here.

Taking into account a drop-out rate of about 20%, a total of 78 patients (26 per group) will be randomized.

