## e) Weight management-related behaviours (T0-T2)

- Self-efficacy (GSES): Sum score
- Impulsivity (BIS/BAS): Two scales: Behavioral Inhibition System (BIS) mean score and Behavioral Activity System (BAS) mean score
- Cognitive emotion regulation (CERQ): Sum scores for nine different conceptual scales: 1) Self-blame, 2) Acceptance, 3) Rumination, 4) Positive refocusing, 5) Planning, 6) Positive reappraisal, 7) Putting into perspective, 8) Catastrophizing and 9) Blaming others

- Emotion regulation (DERS): Global sum score. The six sub-scales will only be reported if there is a significant difference between randomization arms for the global score.
  - Food Craving Questionnaire-Trait (FCO-T-r): Sum score
- f) Mental health (T0-T2)
- Depressive symptoms (PHQ-D): Sum score
  - Anxiety disorder symptoms (PHQ-A): Sum score
  - Quality of life (SF-12): Physical and mental sum scores
- g) Physical health (T0-T2)
- Body mass index (BMI,  $\text{weight}/\text{height}^2 \cdot 10^4$ ), kg/m^2
  - Hip and waist circumference, cm

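### SAP 4.2.2 imputes each continuous secondary score from its whole category, which gives up to 43 predictors for about 62 observed patients in the largest category; cap the predictors and add randomised arm

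*SAP*

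**What the plan says.** SAP 4.2.2 promises means and SDs of the continuous secondary variables both for valid values and after imputation. On the predictors it says: "Imputation variables will include all data from the same" category "of secondary endpoints along with age and sex". It sets no upper limit on their number and no minimum correlation, and it does not list randomised arm or the stratification variables. The only pruning rule is "If the imputation methods should fail to converge, then imputation variables will be successively removed", beginning with the weakest linear correlations.

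The largest category of scores is SAP 2.2 e), dated T0 to T2. It lists "Self-efficacy (GSES): Sum score"; for BIS/BAS, "Two scales: Behavioral Inhibition System (BIS) mean score and Behavioral Activity System (BAS) mean score"; for the CERQ, "Sum scores for nine different conceptual scales"; and one global score each for the DERS and the FCQ-T-r.

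The T1/T0WL linear models are built like the primary model (SAP 4.2.2). The primary analysis is multiply imputed with mice, using 50 imputations (SAP 4.1). For the secondary endpoints the SAP does not name an imputation method, does not say which visits count as data of the category, and does not say whether the linear models are run on imputed data.

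**The concern.** An imputation regression with nearly as many predictors as patients mostly fits noise. A patient who misses a visit usually misses all its scores at once, so many of the predictors for that patient are themselves imputed. The imputed values then follow the patient's own baseline and arm only weakly. Arm contrasts based on them move towards zero and lose precision, so a real effect could be reported as absent. The pruning rule looks at convergence, and an overfitted model can converge. For the primary endpoint the SAP plans a repeat without imputation. For the continuous secondary endpoints it plans only unimputed means and SDs, not an unimputed arm contrast.

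**Working it through.** **Observed patients.** Protocol 7.4.4 randomises 78 patients to leave 63 analysed ("Taking into account a drop-out rate of about 20" per cent). Check: 63 / 0.80 = 78.75, and 78 × 0.80 = 62.4. The stated figures reproduce to within one patient. About 62 patients have T1 data and 16 do not.

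**Predictor count.** Predictors = scores × visits + 2 (age, sex) − 1 (the target).

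- Category e has 1 + 2 + 9 + 1 + 1 = 14 scores. Three visits: 14 × 3 + 2 − 1 = 43. T0 and T1 only: 14 × 2 + 2 − 1 = 29. One visit: 14 + 2 − 1 = 15.
- Category f has 4 scores: 4 × 3 + 2 − 1 = 13. Category g has 3: 3 × 3 + 2 − 1 = 10.
- Category c has 11 raw scores: 11 × 2 + 2 − 1 = 23, or 34 over three visits. Counting the four percentile ranks makes 15 scores, so 31 or 46. The SAP dates this category T0 to T2; Protocol 2.2 and 7.2.2 give t0 and t1 only.
- Category b has about 6 continuous scores over three visits: 6 × 3 + 2 − 1 = 19.

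For 43 predictors and 62 patients: 62 / 43 = 1.4 patients per predictor, 62 − 43 − 1 = 18 residual degrees of freedom, and an R² of about 43 / 61 = 0.70 expected by chance.

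**Simulation.** The documents give no correlations, so these are assumed. Main run: 78 patients, 16 missing completely at random and losing all T1 and T2 scores, true effect 0.5 SD, correlation 0.6 within a score over time and 0.3 between scores, predictive mean matching with 5 donors, 20 imputations, ANCOVA pooled by Rubin's rules. The small model holds the score's own baseline, the stratification factors, age and arm. Three other runs differ in detail; for example, in the 800-trial run missingness depends on baseline. All entries below include arm (absolute estimate, mean SE, power).

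| Run | 43 predictors | Small model | Observed-case ANCOVA |
|---|---|---|---|
| Main (150 trials for 43 predictors, else 300) | 0.404, 0.276, 26% | 0.468, 0.217, 56% | 0.482, 0.221, 57% |
| 800 trials | 0.41, 0.27, 28% | 0.48, 0.21, 60% | 0.50, 0.22, 62% |
| 200 trials | 0.39, 0.28, 19% | 0.47, 0.22, 57% | 0.48, 0.22, 56% |
| 150 trials | 0.39, 0.26, 26% | 0.46, 0.22, 54% | 0.48, 0.22, 55% |

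Main run: 1 − 0.404 / 0.468 = 14% and 1 − 0.404 / 0.482 = 16% shrinkage; SE ratios 0.276 / 0.217 = 1.27 and 0.276 / 0.221 = 1.25. Over all runs the shrinkage is 14 to 19% and the SE increase 18 to 29%. The Monte Carlo error of the 0.404 is 0.019.

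**29 predictors, with arm.** 0.438, SE 0.239, against 0.487, SE 0.219 (small) and 0.501, SE 0.222 (observed). The effect is 10 to 13% smaller and the SE 8 to 9% larger. This rests on 60 trials (Monte Carlo error 0.027), so it is less certain.

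**13 predictors, with arm.** 0.495, SE 0.221, against 0.506, SE 0.218 for the small model: no material harm. Categories b and c were not simulated.

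**Role of arm (main run).** Without arm, the 43-predictor model gives 0.386, SE 0.262, and the small model 0.378, SE 0.217. Trimming alone repairs the SE but leaves the estimate about 0.1 below the observed-case value.

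**Only the target score missing.** 43 predictors with arm: 0.445, SE 0.246, so the shrinkage falls to 1 − 0.445 / 0.468 = 5% against the small model.

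**The case against.** **The linear models may not use imputed data.** SAP 4.2.2 ties imputation expressly only to means and SDs. This stands as a condition on the arm-contrast result. The shared structure with the imputed primary model, and the full analysis set as basis, make imputation the natural reading. On the narrow reading, the post-imputation means and SDs still come from this model. The T0 to T2 mixed model for the intervention groups, fitted by REML, can use incomplete patients without imputation.

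**It is not all secondary endpoints.** A reader might take 43 predictors as typical. It is the largest category under one reading of the visits. A count of 61 is also possible if the six DERS sub-scales enter, but SAP 2.2 e) reports those only after a significant global result and does not say that they join the imputation.

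**The fallback might work.** A reader might infer that it would never fire. The documents do not settle that: non-convergence is undefined and no imputation method is named. Under normal-model imputation the main run gave SEs above 1.2, which trace plots might expose. With predictive mean matching the runs completed. What stands is that the trigger is not designed to detect overfitting.

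**The stakes are limited.** Protocol 7.5.2 calls these outcomes exploratory and descriptive, although SAP 1 speaks of confirmatory analysis of primary and secondary endpoints. The error is conservative: interval coverage was 98% in the 800-trial run. Missingness may also be below 20%, because the protocol keeps assessing patients who stop treatment, and the SAP removes from the full analysis set control patients who missed T0WL because of SARS-CoV-2.

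**Conclusion.** The point holds for the larger categories: e, and to a lesser degree c. With 43 predictors for about 62 patients, and if the T1/T0WL models use the imputed data, the arm effect shrinks by about 15 to 20% and its SE rises by about 25%. That is worse than analysing the observed cases. With 29 predictors the loss is about 10 to 13% in the effect and about 10% in the SE. Categories f and g are not materially affected.

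These sizes assume correlations of 0.6 over time and 0.3 between scores, about 20% missing T1, and predictive mean matching; 62 is a planning figure. The documents do not support a claim that every secondary endpoint is affected, that the fallback cannot fire, or that too many predictors alone explain the bias of the plan as written. The unlisted arm gives a similar shrinkage even in a small model, so both changes are needed.

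**What to change.** Replace the predictor sentence in SAP 4.2.2 by:

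> Each score is imputed from randomised arm, the stratification variables, age, sex, the same score at the other visits, and a small capped number of further variables chosen by correlation (e.g. at most three, by quickpred).

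Let this cap replace the convergence-only pruning rule. List the visits that enter, name the imputation method, and state whether the T1/T0WL linear models use the imputed data. Report the baseline-adjusted ANCOVA on observed data alongside.

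The cost is SAP wording, one predictor matrix in the imputation code and one extra set of model results. The downside is that some auxiliary information goes unused. The cap of three is a convention; another small number would serve.

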### 2.2 Secondary endpoints (Item 6a of the CRED-nf checklist)

Unless otherwise indicated, the scores from questionnaires are calculated using the “qscorer” package from [name] (see appendix for code). Comparisons between all three groups are foreseen at T0 (baseline) and T1/T0WL. After T0WL, the WL control group received an fNIRS intervention. Hence, T2 can only be used to estimate changes within a group and between the two intervention groups.

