### 4.1 Primary endpoint

The primary endpoint, the number of OBEs at post-assessment or post-waiting, will be analysed using ANCOVA with OBEs as the dependent variable, OBEs at T0 as a covariate as well as the stratification criteria (`strabmi`, `stralsex`, `strawei`). The code for this test will have the structure

```
anova(lm(OBE_FU ~ OBE_T0 + STRABMI + STRASEX + STRAWEI + ARMS)).
```

The variables OBE\_FU and OBE\_T0 will be shifted by the mean of OBE at T0 so that the intercept in the model reflects change in time. A closed-testing procedure will be used, meaning

---

 The planned dates are as follows: session 1/2 (week 1), session 3/4 (week 2), session 5/6 (week 3), session 7/8 (week 4), session 9 (week 5), session 10 (week 6), session 11 (week 7), session 12 (week 8),

that the initial comparison will be between the two intervention groups combined and the waiting group and the three pair-wise tests (fNIRS vs. wait control group, EEG vs. wait control group and fNIRS vs. EEG group) will be performed without adjustment if the global test is significant. If the global test is not significant, estimates and confidence intervals will still be provided for the contrasts in OBE, but no formal statistical test will be carried out. Estimates will be taken from the linear model and a Wald confidence interval will be used. Moreover, secondarily, the analogous analysis with effect size will be performed.

Missing data will be treated with multiple imputation using the R package “mice” (van Buuren and Groothuis-Oudshoorn 2011). The imputation variables will include the answer to the question “In how many of the situations in which you ate too did you feel you had lost control of your eating behaviour” (pre72). Sex, BMI and the stratification variable participation in a weight-loss programme will also be used. Fifty imputations will be performed.

To test the robustness of the results, the primary analysis will be repeated without imputation and pessimistic and optimistic scenarios will be considered.

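### The T0-T1-T2 mixed model leaves the T0 arm means free, so its fNIRS-EEG contrasts at T1 and T2 are not baseline-adjusted, and its covariance sentence is ambiguous

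*SAP*

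**What the plan says.** SAP 4.2.2 sets out two models for continuous secondary outcomes.

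- **Three arms, one time point.** "Variables at T1/T0WL will be analysed with linear models having the same structure as for the primary endpoint". SAP 4.1 defines that structure as "OBEs as the dependent variable, OBEs at T0 as a covariate as well as the stratification criteria", which is an ANCOVA with the T0 value as covariate.
- **Two arms, three time points.** "Data for T0, T1 and T2 will be analysed for the intervention groups in a mixed model". Besides the stratification variables, "time and group will be treated as fixed effects including the interaction between group and time". On the covariance: "The patient ID will be treated as a random term", followed by "The model will be fit using restricted maximum likelihood (REML) and an unstructured variance-covariance matrix".

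The second model has no T0 covariate and no constraint that the arms share a T0 mean. The text does not say which matrix is unstructured or which contrast is reported at T2. It also gives no fallback if the fit fails, although SAP 4.2.1 has one for the logistic regression and SAP 4.2.2 has one for the imputation.

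SAP 2.2 explains the role of the last visit: "T2 can only be used to estimate changes within a group and between the two intervention groups". SAP 4.2.1 rules out formal testing of abstinence and remission at T2.

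**The concern.** The longitudinal model is the only formal comparison of fNIRS with EEG neurofeedback at six months. With T0 in the outcome vector and free arm means, it offers two between-arm contrasts at T2: the difference in change from T0 (the group-by-time term) and the plain T2 difference. Neither adjusts for baseline. If the arms differ by D at T0 by chance, and the T0-T2 correlation is ρ with equal variances, the plain difference carries ρD of that imbalance. The change score over-corrects by (1−ρ)D. Both are unbiased over repeated randomisations, but they spend precision that an adjusted contrast keeps.

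The plan is also inconsistent with itself. For the same variable, the fNIRS-EEG difference at T1 can come adjusted from the ANCOVA or unadjusted from the mixed model, and no rule says which one stands.

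A second, smaller matter is that the patient term and the unstructured matrix are prescribed side by side without saying how they combine. On one natural reading the specification has one parameter too many.

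**Working it through.** The documents give no figure for this model, so there is none to reproduce.

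**Inputs**
- Three visits and two arms: SAP 4.2.2.
- Arm size: "a total of 78 patients (26 per group) will be randomized" (protocol 7.4.4). The same section counts 42 analysed in the two intervention arms, which is 42/2 = 21 per arm.
- Correlation ρ between T0 and T2: not in the documents, assumed 0.2 to 0.8.
- Further assumptions: equal variance σ² across visits and arms, complete data, and covariance treated as known. The last ignores the small cost of estimating the T0 slope.

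**Variance of the T2 arm contrast, n per arm**
- Plain T2 difference: σ² · 2/n
- Difference in change from T0: 2σ²(1−ρ) · 2/n
- Baseline-adjusted (T0 covariate or common T0 mean): σ²(1−ρ²) · 2/n

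The variance ratio of adjusted to plain is 1−ρ². The ratio of adjusted to change is (1−ρ²)/[2(1−ρ)] = (1+ρ)/2.

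| ρ | ratio to T2 difference | ratio to change score | reduction against the better of the two | SE at n = 21, in SD (T2 difference / change / adjusted) |
|---|---|---|---|---|
| 0.2 | 0.96 | 0.60 | 4% | 0.309 / 0.390 / 0.302 |
| 0.3 | 0.91 | 0.65 | 9% | 0.309 / 0.365 / 0.294 |
| 0.4 | 0.84 | 0.70 | 16% | 0.309 / 0.338 / 0.283 |
| 0.5 | 0.75 | 0.75 | 25% | 0.309 / 0.309 / 0.267 |
| 0.6 | 0.64 | 0.80 | 20% | 0.309 / 0.276 / 0.247 |
| 0.7 | 0.51 | 0.85 | 15% | 0.309 / 0.239 / 0.220 |
| 0.8 | 0.36 | 0.90 | 10% | 0.309 / 0.195 / 0.185 |

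At ρ = 0.5, for example, the adjusted SE is √(0.75 × 2/21) = 0.267. Because √0.75 = 0.87, the interval is about 13% narrower than either unadjusted one.

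**Missing T2 data.** Generalised least squares was run with 26 per arm, 5 per arm missing T2, both T0 correlations 0.5 and a T1-T2 correlation of 0.6. The SE is 0.2961 for either unadjusted contrast and 0.2616 adjusted, a variance ratio of 0.78 instead of 0.75.

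**Size of chance imbalance.** With 26 per arm, the T0 difference has SE √(2/26) = 0.28 SD.

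**Covariance parameters.** Three visits give 3 variances + 3 covariances = 6 distinct elements. The possible readings are:
- random intercept plus unstructured residual matrix: 1 + 6 = 7 parameters, rank 6, redundant;
- unstructured random visit effects plus a residual variance: 6 + 1 = 7, rank 6, redundant;
- unstructured residual matrix with patient only as grouping factor: 6 of 6, identified;
- random intercept and slope with unstructured random-effects matrix plus residual variance: 4, rank 4, identified;
- random intercept and residual variance only: 2, rank 2, identified, but with nothing left to structure.

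The redundancy in the first reading does not come from having three visits. It is 11 against 10 at four visits and 22 against 21 at six.

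**Effect on the contrasts.** One data set was simulated with 2 × 21 patients, three visits and about 20% missing T2. REML fits of the 7-parameter model from three starting values gave patient variances of 0.004, 0.060 and 0.147. In all three the log-likelihood was −41.3026, the T2 difference −0.9445 and its SE 0.3075, the same as in the 6-parameter model. Only the split of variance was arbitrary.

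**The case against.** The strongest reply is that this is a valid model and a matter of preference. Free T0 means are unbiased under randomisation, and T0 as an outcome serves both uses that SAP 2.2 gives to T2, including within-group change. Protocol 7.5.2 describes the further secondary outcomes as exploratory and descriptive. All of that is true, and it limits the point to precision and consistency. It does not explain why the same variables are baseline-adjusted at T1/T0WL and unadjusted at T2.

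A reader might infer more than the documents support:

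- *That the model cannot be identified because there are only three visits.* The sentence does not say which matrix is unstructured, several readings are identified, and the redundant reading is redundant at any number of visits.
- *That the follow-up comparisons may be unobtainable.* Warnings or non-convergence are possible, but a converged fit gives the same contrasts.
- *That the baseline is thrown away.* The group-by-time contrast uses it, though less efficiently.
- *That the gain is the full (1+ρ)/2 ratio.* That compares only with the change score. At ρ = 0.3 it suggests a 35% variance saving, but against the plain T2 difference the saving is 9%.
- *That forcing a common T0 mean has no downside.* The FAS in SAP 3.1 is partly selected after randomisation. Patients whose fNIRS measurement failed for technical reasons are left out (three were replaced). Those whose intervention was cut short by the pandemic stay only with at least 5 sessions and T1 binge-eating data.

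**Conclusion.** The point holds as one of precision and consistency. The between-arm contrasts at T1 and T2 from the longitudinal model are not baseline-adjusted, and the SAP does not name the one to report. For T2, adjustment lowers the variance by 4% to 25% relative to the better unadjusted contrast. The gain is largest at ρ = 0.5 and smallest at ρ = 0.2. This rests on an assumed ρ, equal variances and complete data; moderate dropout shrinks it slightly. If the less efficient contrast were reported, the loss would be larger: the ratio falls to 0.65 for the change score at ρ = 0.3 and to 0.51 for the T2 difference at ρ = 0.7.

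The covariance wording is mainly a matter for clarification. On the redundant readings the variance components are arbitrary and fitting may be troublesome, but the arm contrasts from a converged fit do not change.

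Only the two-arm longitudinal model for continuous secondary outcomes is affected. The primary analysis and the three-arm T1/T0WL comparisons already adjust for T0.

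**What to change.** In SAP 4.2.2, for the between-arm contrasts:

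1. Use T1 and T2 as outcomes and T0 as a covariate, allowing a T0-by-visit term, with group, visit, group-by-visit and the stratification variables. A common T0 mean for the two arms is an alternative only if the analysed set is accepted as randomised despite the exclusions in SAP 3.1. The covariate form is the safer choice.
2. State that the unstructured matrix is the residual covariance, with patient as the grouping factor and no additional random intercept.
3. Name the adjusted fNIRS-EEG difference at T2 as the reported contrast, and say which model supplies the T1 difference.
4. Add a convergence fallback, as the SAP already does for the logistic regression and the imputation.

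Within-group change from T0 can still be reported alongside.

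The cost is a changed model formula and a few lines of text, with no new data. The common-mean version would also rely on randomisation in a partly selected set. SAP 4.3 already foresees a further SAP version that could carry the change.

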### 4.3 Analysis of fNIRS data

Certain aspects of the analysis of fNIRS data have not yet been clarified so that we now present only a temporary plan to be updated in the next version of the SAP.

The pre-processing of the fNIRS data follows standard procedures and is described below (appendix 6.11). After converting the raw data to haemoglobin concentrations, these are analysed in a general linear model (GLM) where they are treated as the dependent variable with the predicted time course as the independent variable (design matrix). The model estimates a weighting for this predicted time course (referred to here as  $\beta$ ).

The ability of the GLM to model the data may be very limited. In such cases, the type I error is not likely to be inflated, but the type II error can be extremely large, i.e. regardless of the effect size, the model will have very low power. If the mean explained variance of the GLM at baseline is below 15%, then the model will be deemed inadequate and will not be used.

In the standard pre-processing pipeline, outliers are identified on the task and section level and removed. The number of such data (participants) will be reported by session and task (Item 3e of the CRED-nf checklist) and in sensitivity analyses their effect will be studied.

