#### 4.3.1 Regulation success based on the feedback signal (CRED-nf 5a)

A graphical depiction for summary statistics of the raw data for each session in the regulation condition will be provided for the following variables

- percentage success defined to be the number of sample points with online oxygenated haemoglobin values were smaller than the predecessor divided by the total number of sampling points (roughly  $10^5$ ). This is a surrogate for the proportion of time for which the patient experienced “success” though a maximum/minimum picture size could not be exceeded and each step was so small that it could not be perceived.
- minimum picture size (12 per patient) as one measure of success for the feedback
- mean picture size (12 per patient) as a second measure of success for the feedback

Transfer condition

- a graphical representation as with the regulation condition will be provided

Note that after session 6, the selection of pictures was changed to avoid habituation effects.

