#### 4.3.2 Within-session and between-session comparisons (CRED-nf 5b/5c)

The  $\beta$ -values for the two particular channels of each patients' individual ROIs will be analysed. Since the predicted time course in the first and second half of the regulation block and also between blocks is identical, a comparison of  $\beta$  amounts to a comparison of the optimal weighting of this predicted time course. As noted above, this can be difficult to interpret: e.g. an increase from 0.8 to 1 could indicate that the response followed the expectation both times with an increase in amplitude from 0.8 to 1, but it is also conceivable that there was good response to the stimulus the first time and none whatsoever with the higher value of  $\beta$ .

- $\beta$  will be displayed graphically for the first and second half of the average of all sessions
- The two  $\beta$  values per session will be averaged and displayed graphically per sessions
- $\beta$  will be analysed after standardization in a mixed linear model with the coefficients as the dependent variable. For the within-session analysis, the first and second half of the regulation condition will be estimated (fixed effect) and session (linear fixed effect) and patient as a random effect for the intercept. For comparisons between the tasks regulation and mirror, a mixed model with condition as the fixed effect of interest, session and first/second half as a nuisance parameter and patients as a random term will be used. These analyses will be repeated for the transfer vs mirror condition.

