### **4.3.3 Correlation between regulation and outcomes for patients who provided data for at least two feedback sessions (CRED-nf 6b)**

A linear model will be used with the number of OBEs at post-assessment as the dependent variable, the value at T0 as covariate and mean picture size across all sessions as the variable of interest.

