#### First Level Analysis

A GLM was calculated for each channel, each half (first/second half of NF), each condition (feedback/transfer/mirror) and each session of each participant, modelling event-related concentration changes with a canonical hemodynamic response via the toolbox's function *GLM* (leaving the type at the default option AR-IRLS). The general linear equation was solved with an iteratively auto-regressive whitened, weighted least-squares method (AR-IRLS) (Barker et al. 2013). This model applies an  $n^{\text{th}}$ -order AR filter derived via an Akaike model-order selection to whiten both sides of the GLM expression. All source-detector pairs within a file are solved concurrently yielding a full covariance model of the noise. The AR-IRLS method accounts for the expected presence of serially correlated errors (i.e., extracerebral components) in the optical signals due to cardiac pulsation and respiration and has been shown to have a good control of type-I error (Huppert 2016). It is not recommended to filter data if using the AR-IRLS GLM algorithm (Huppert 2016). To ensure data quality, all data were visually inspected before and after applying the AR-IRLS method.

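### A small brain response before training could, through the 15% rule in SAP 4.3, remove every formal beta test of fNIRS regulation, and no replacement is named

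*SAP*

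**What the plan says.** SAP 4.3 models each haemoglobin series with one predicted time course and takes its weight, beta, as the quantity to analyse. It warns that the model may describe the data poorly and that in such cases, "regardless of the effect size, the model will have very low power". The rule follows: "If the mean explained variance of the GLM at baseline is below 15%, then the model will be deemed inadequate and will not be used".

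The SAP does not derive the 15%. It does not say whether baseline means the localizer, the T0 visit or the first training session, nor over which fits the mean is taken. According to the First Level Analysis paragraph of the fNIRS preprocessing appendix, "A GLM was calculated for each channel, each half (first/second half of NF), each condition (feedback/transfer/mirror) and each session of each participant", so there are many candidate averages.

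The formal tests that depend on this model are in SAP 4.3.2, where beta "will be analysed after standardization in a mixed linear model with the coefficients as the dependent variable". They compare first and second half, estimate a session trend, and compare regulation with mirror and transfer with mirror. The CRED-nf table in the appendix assigns item 5c, the statistical comparison with a control condition, to 4.3.2 for fNIRS and 4.4.2 for EEG. The EEG section has no comparable rule.

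Section 4.3 declares itself provisional: "we now present only a temporary plan to be updated in the next version of the SAP".

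**The concern.** An adequacy check should detect a wrongly shaped predicted time course. R² from a one-regressor fit does not isolate that. It falls when the shape is wrong, and equally when the shape is right but the response is small next to physiological noise. It is also blind to sign, so a strong response in the unwanted direction passes.

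Training is meant to change the response over sessions, yet the decision rests on the start alone. A small initial response that grows is the pattern the session analysis should be able to show, and under the rule that analysis may never be run. The experimental arm could then have no formal within-session or between-session test of regulation, while the EEG comparator keeps its mixed models and paired tests. Any replacement would be chosen after seeing the data.

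**Working it through.** **Inputs from the documents.** The cut-off is 15% and there is one predicted time course (SAP 4.3). There are 26 patients per arm (protocol synopsis), and 63/3 = 21 per arm analysed (protocol 7.4.4). The cut-off comes without a derivation or a firing probability, so there is no figure to reproduce.

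**Assumed, because the documents give none.** The effective number of independent observations per fit (n_eff), block lengths, noise autocorrelation, a response share common to all patients, and R² on the raw scale. The SAP fits by AR-IRLS and does not say whether R² is raw or whitened.

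**Step 1: what R² measures.** Let the response take a share S of the variance, and let its true time course correlate ρ with the predicted one. Then the expected R² is about ρ² × S. A perfect shape with a 5% share gives 1² × 0.05 = 5%. A poor shape (ρ = 0.5) with a 20% share gives 0.25 × 0.20 = 5%. The rule cannot separate the two, and squaring removes the sign.

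**Step 2: no response.** R² follows Beta(1/2, (n_eff − 2)/2) with mean 1/(n_eff − 1). Simulated probability that the mean over 26 patients is below 15%:

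| n_eff | mean R² | P(rule fires) |
|---|---|---|
| 6 | 20% | 0.12 |
| 8 | 14.3% | 0.61 |
| 10 | 11.1% | 0.92 |
| 12 | 9.1% | 0.99 |
| 20 or more | 5.3% or less | 1.00 |

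**Step 3: a true response, correctly shaped.** R² = A/(A + B), with A noncentral chi-square on 1 df, noncentrality n_eff × S/(1 − S), and B chi-square on n_eff − 2 df. For S = 5% and n_eff = 20 the noncentrality is 20 × 0.05/0.95 = 1.05, the mean R² is 9.8%, and the rule fires with probability 0.99.

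| True share | n_eff 10 | 20 | 50 | 100 |
|---|---|---|---|---|
| 5% | 0.49 | 0.99 | 1.00 | 1.00 |
| 10% | 0.11 | 0.60 | 0.98 | 1.00 |
| 15% | 0.01 | 0.07 | 0.19 | 0.27 |
| 20% | ≤0.001 | ≤0.001 | ≤0.001 | ≤0.001 |

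A cross-check used explicit block designs: 3–12 blocks, 15–30 s on, 15–20 s off, AR(1) noise with correlation time 2–10 s, and 26 patients. The firing probability was 1.00 at a 0% share, 0.99–1.00 at 5%, 0.55–1.00 at 10%, 0.04–0.31 at 15% and 0.00 at 20%.

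**Step 4: does low baseline R² rule out detecting change?** Take a simplified paired comparison of first and last session, with the shape correct. In noise-SD units beta = √(R²/(1 − R²)). If R² goes from 0% to 8.3%, the change in beta is √(0.083/0.917) = 0.301. With n_eff = 20 and a between-patient SD of change of 0.4, the SD of one patient's change is √(2/20 + 0.4²) = 0.510. With 21 patients the noncentrality is (0.301/0.510) × √21 = 2.70, and two-sided power at 5% is about 73%. Across 21–26 patients, n_eff 20–100, SD 0.2–0.4, baseline R² 0–1% and final R² 8–15%, power ran from about 72% to 100%. In the worked case the rule would have fired with probability 1.00 (step 2, n_eff = 20).

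**Step 5: what depends on the GLM.**
- Lost if the rule fires: the beta displays and all mixed models of 4.3.2.
- Kept: the per-session graphs of 4.3.1, including "mean picture size (12 per patient) as a second measure of success for the feedback", and the 4.3.3 regression of binge-eating episodes, with "mean picture size across all sessions as the variable of interest". The first is descriptive. The second averages over sessions, so it cannot test change across them.
- Also kept: the haemoglobin values by condition, block and task listed in SAP 2.2 d). No formal model is planned for them.

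**The case against.** The best defence is that an adequacy rule fixed in advance is legitimate. SAP 4.3.2 itself explains that beta is hard to interpret when fit is poor. Read in context, the remark on power concerns a predicted course that does not match the data. If the shape is wrong, a larger response need not raise beta. Step 4 assumes a correct shape and cannot refute that remark. It shows only that low R² does not by itself establish the misfit the SAP fears. This part of the defence stands.

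A reader might also infer that the rule fires almost surely because untrained patients cannot yet regulate. The documents do not support that. Being unable to regulate is not the same as showing no task-locked response. Patients view appetitive food pictures during the task, the protocol (1.2.1) picks an area that already responds to food cues, and the SAP picks channels on localizer t-values. At a 20% share the rule practically never fires. If baseline means the localizer, ability to regulate does not enter at all. Equally, nothing guarantees 15%: the SAP localizer is a different task (Go/NoGo against passive viewing), and the SAP sets no minimum t-value.

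Finally, the stakes are limited. SAP section 4 calls these analyses explorative, section 4.3 is marked provisional, and the primary endpoint is untouched. That lowers the weight of the point. It does not supply the missing fallback.

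**Conclusion.** The concern holds in a conditional form. Baseline R² alone decides whether any formal beta test of fNIRS regulation is run, and it mixes response size with shape fit. With a task-locked share of about 5% or less before training, the rule very probably fires (0.99 or more for n_eff of at least 20, and in every block design tried). With very few effective observations this weakens: 0.49 at a 5% share and n_eff 10. At 10% the outcome depends on the design, and at about 20% the rule practically never fires. These figures rest on assumed timing, noise and a common response size. The documents do not show which case applies.

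It would be too strong to say that the fNIRS learning analysis as a whole is abandoned, because 4.3.1, 4.3.3 and the listed haemoglobin outcomes survive. What would be missing is a formal test of change within or between sessions, and of regulation against mirror. This is a cheap improvement to an exploratory section and no threat to the trial's main result.

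**What to change.** In the announced next SAP version:

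1. Always fit the 4.3.2 mixed models to a shape-free outcome as well: mean oxygenated haemoglobin in the regulation window minus the preceding rest, and minus mirror. The values are already listed in SAP 2.2 d).
2. Do not let baseline R² alone remove the beta models. Report them with mean R² by session. When fit is low, label them as poorly fitting and secondary to the shape-free result.
3. If a gate is kept, define baseline and the set of fits averaged, state whether R² is raw or whitened, justify the cut-off, base it on fit across sessions, and name the shape-free model as the fallback.
4. State the expected direction of the contrast. SAP 4.3.1 counts falling oxygenated haemoglobin as success, while the Visual Feedback Signal paragraph gives rising values as the goal. These must be reconciled.

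The cost is SAP wording and one extra exploratory model on data already processed. The downside is that a poorly fitting GLM may be reported, with its R² beside it.
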